#### **3.4.2.2 Disease Control**

Disease control rate (DCR) is defined as the proportion of subjects with a BOR of confirmed CR, confirmed PR, or SD (maintained for  $\geq 8$  weeks [-3 days]). Duration of SD is defined as the time from the first dose of investigational product until the first documentation of disease progression or death due to any cause, whichever occurs first, and will allow for the protocol-defined disease assessment window of  $57 \pm 3$  days for first post dose disease assessment. DCR will be estimated with a 95% CI using the exact binomial distribution. DCR will also be summarized by T790M status based on tumor biopsies and plasma T790M status at baseline (determined by a central lab) with a 95% CI estimated using the exact binomial distribution.

#### **3.4.2.3 Duration of Response**

Duration of response (DOR) is defined as the time from the first documentation of a subsequently confirmed objective response until the first documentation of disease progression or death due to any cause, whichever occurs first regardless of whether the subject receives subsequent anticancer therapy prior to progression. For subjects who are alive and progression-free at the time of data cut-off for analysis, DoR will be censored at the last tumor assessment date. Only subjects who have achieved objective response (confirmed CR or confirmed PR) will be evaluated for DOR. DOR is defined in months as follows:

$DOR \text{ (months)} = (\text{Date of PD/death or censoring} - \text{Date of first confirmed disease response} + 1) / (365.25/12),$

The date of PD/death or censoring is the same as defined for PFS. The median DOR and its 95% CI will be estimated using the Kaplan-Meier method.

#### **3.4.2.4 Progression-free Survival**

Progression-free survival (PFS) is defined as the time from the first dose of investigational product until the first documentation of a disease progression or death due to any cause, whichever occurs first, regardless of whether the subject receives subsequent anticancer treatment prior to progression. Patients who have no documented progression and are still alive at the time of analysis will be censored at the time of the latest date of assessment from their last evaluable RECIST 1.1 assessment. PFS is defined in months as follows:

$PFS \text{ (months)} = (\text{Date of PD/death or censoring} - \text{Date of the first dose of investigational product} + 1) / (365.25/12),$

The censoring guidance and the date of PD/death or censoring are given in the table below. The number and percentage of patients experiencing a PFS event and Kaplan-Meier plots of PFS will be presented by treatment group. The median PFS and its 95% CI will be estimated using the Kaplan-Meier method. The proportion of subjects progression free and alive at time points of interest months (such as 3 months and 6 months) and associated 95% CI will be estimated using the Kaplan-Meier method.

**Table 3.4.2-1 Summary of Censoring Guidelines for PFS**

Situation	Date of PD/Death or Censoring	PFS Outcome
Documented Progressive Disease (PD) or death	Date of earliest sign of PD or death, whichever comes first	Event (unless the censoring rule specified below)
Death or PD immediately after $\geq 2$ consecutive missed or non-evaluable disease assessments as per the protocol specified assessment schedule	Date of last progression-free disease assessment prior to missed or non-evaluable assessments, or the first dose of investigational product, whichever occurred last	Censored
No PD or death at time of analysis or lost to follow-up	Date of last adequate progression-free disease assessment	Censored
No tumor assessment at baseline and no evidence of PD at first post-baseline disease assessment OR No tumor assessment post-first dose, and no death prior to second scheduled post-baseline disease assessment	Date of the first dose of investigational product	Censored

PD = progressive disease; PFS = progression-free survival

Subjects having missing lesion data at baseline or no disease assessments post-first dose of investigational product will have PFS censored at the date of the first dose of investigational product unless the subject dies prior to the second scheduled post-baseline disease assessment in which case the death date will qualify as a PFS event.

If a subject has two or more consecutive completely missed or non-evaluable assessments followed immediately by death or an assessment showing radiologic disease progression, then the subject will be censored for PFS. PFS will be censored at the date of the first dose of investigational product or the last progression-free disease assessment prior to the missed or non-evaluable assessments, whichever occurred last.

If a subject has two or more consecutive missed or non-evaluable assessments followed by an assessment showing no radiologic disease progression, then the assumption will be that the subject did not progress during the missed or non-evaluable assessments. Two or more consecutive assessments is defined as  $\geq 16$  weeks plus 6 days (two disease assessments as per protocol plus a 6 days visit window to allow for a late assessment) after the last evaluable post-baseline disease assessment.

Subjects remaining on study without radiologic disease progression or death at the time of analysis will be censored for PFS at the date of their last adequate disease assessment. An adequate assessment is one that has recorded measurements for all target lesions defined at

baseline and a non-NE non-target lesion response (ie, the last non-missing or non-evaluable disease assessment).

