#### 7.1.5 Assignment of Dates of Disease Progression or Disease Response

For all analyses of endpoints resulting from an application of RECIST 1.1 to investigator assessed tumor measurements, there may be cases in which disease assessments span a series of dates. For establishing the start date of a subsequently confirmed response in which the disease assessment spans multiple days, the date of response assigned will be the latest date of evaluations corresponding to the disease assessment. The date of latest evaluation will also

be assigned for a mid-study assessment showing SD as the date assigned for the purposes of censoring duration of response, TTP and PFS.

The date of PD will be the first date at which any objective diagnostic test provides data indicating PD. Specifically, for RECIST 1.1 the date of PD will be the earliest of the following 3 evaluation dates:

- Date of PD as indicated by target lesions: If PD is triggered by a change in sum of diameters of target lesions, and the dates of evaluation of the target lesions vary for the same assessment, assign the first evaluation date among target lesions.
- Date of PD as indicated by non-target lesions: If the dates of evaluation of the non-target lesions vary for the same assessment, assign the first evaluation date for which any non-target lesion exhibits a status of Unequivocal Progression.
- Date of PD as indicated by new lesions: If multiple new lesions are identified and the dates of evaluation for the new lesions vary for the same assessment, assign the first evaluation date for which any new lesion is detected.

In scenarios where the Investigator disease response is either a response or PD, and differs from that of the application of RECIST 1.1 to investigator assessed tumor measurements separate response and/or progression dates will be required. Determination of the start date of a subsequently confirmed response in which the disease assessment spans multiple days remains the same as described previously. Specifically, the date of response assigned will be the latest date of evaluations corresponding to the disease assessment. The date of PD will be the earliest date of evaluations corresponding to the disease assessment.

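### For a subject with no baseline tumor assessment and progression at the first post-baseline assessment, SAP Table 3.4.2-1 records a PFS event while the paragraph below it censors at first dose

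*SAP*

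**What the plan says.** SAP Section 3.4.2.4 runs PFS from first dose "until the first documentation of a disease progression or death due to any cause, whichever occurs first". It refers to Table 3.4.2-1 for the censoring guidance and dates.

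In that table:
- Row 1 makes documented PD or death an "Event (unless the censoring rule specified below").
- Row 4 censors at the date of first dose and has two limbs joined by OR. The first limb is "No tumor assessment at baseline and no evidence of PD at first post-baseline disease assessment". The second is "No tumor assessment post-first dose, and no death prior to second scheduled post-baseline disease assessment".

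The paragraph directly under the table restates the rule: "Subjects having missing lesion data at baseline or no disease assessments post-first dose of investigational product will have PFS censored at the date of" first dose, "unless the subject dies prior to the second scheduled post-baseline disease assessment in which case the death date will qualify as a PFS event".

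The two statements differ in three ways:
- The paragraph has no condition on PD at the first assessment.
- The paragraph applies the early-death exception to both groups, whereas row 4 writes it only after the OR.
- The table speaks of having no tumor assessment at baseline. The paragraph speaks of missing lesion data, which could also cover partly missing data.

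**The concern.** A programmer has two instructions for the same subject and no statement of which prevails. If the paragraph is followed, a documented early progression leaves the PFS risk set on Day 1. That censoring depends on nothing but missing baseline data and overrides a known failure, so it makes PFS look better than it was. The study is open-label (SAP Section 2.3), so a choice left open in the plan could be settled after outcomes are known.

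The situation is foreseeable under the SAP's own rules:
- PFS is summarized in the as-treated population, which requires only receipt of investigational product (Table 3.2-1, Section 3.4.2).
- Section 3.4.2.1 expressly provides for subjects with missing baseline lesion data.
- PD does not require baseline measurements. A new lesion gives PD whatever the target and non-target responses (Section 7.1.3), and for its date the SAP says to "assign the first evaluation date for which any new lesion is detected".

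**Working it through.** The SAP gives no figure to reproduce, so the check sets the two rules side by side. Inputs are rows 1 and 4 of Table 3.4.2-1 and the paragraph below it. For a subject with no baseline assessment, three facts matter: whether there is a post-dose assessment, whether the first one shows PD, and whether death occurs before the second scheduled assessment.

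Row 4 can be read in two ways. In reading A, the no-death condition belongs to the second limb only. In reading B, it covers both limbs.

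| Pattern (no baseline assessment) | Table, reading A | Table, reading B | Paragraph |
|---|---|---|---|
| 1. PD at first assessment, no early death | Event at PD | Event at PD | Censored at first dose |
| 2. Assessed, no PD, early death | Censored at first dose | Event at death | Event at death |
| 3. No post-dose assessment, early death | Censored at first dose | Event at death | Event at death |
| 4. Assessed, no PD, no early death | Censored at first dose | Censored at first dose | Censored at first dose |
| 5. No post-dose assessment, no early death | Censored at first dose | Censored at first dose | Censored at first dose |
| 6. PD at first assessment, then early death | Event at PD | Event at PD | Event at death |

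Pattern 1 conflicts under both readings. Patterns 2 and 3 conflict only under reading A. Patterns 4 and 5 agree throughout. In pattern 6 both rules give an event, but on different dates.

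**Recorded time in pattern 1.** Section 3.4.2.4 gives PFS (months) = (end date − first dose date + 1) / (365.25/12), and 365.25/12 = 30.4375. The first assessment is due on Day 57 ± 3 (Section 3.4.2.1).
- Table: event at 57/30.4375 = 1.87 months (54/30.4375 = 1.77 to 60/30.4375 = 1.97).
- Paragraph: censored at 1/30.4375 = 0.03 months.

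**Illustration of the effect on 6-month PFS.** The SAP does not say how many subjects would be affected, so k below is an assumption, as is the median. Take n = 46 (the Arm A maximum) and no other censoring before 6 months, and let S be 6-month PFS among the other 46 − k subjects.
- Paragraph rule: the estimate is S, because the k subjects leave on Day 1.
- Table rule: the estimate is (46 − k)S/46, because the k subjects are early events.
- Difference: kS/46.

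With exponential PFS, S = 2^(−6/4) = 0.354 for a median of 4 months and 2^(−6/6) = 0.500 for a median of 6 months.
- k = 0: difference 0.
- k = 1: 0.354/46 = 0.8 to 0.500/46 = 1.1 percentage points.
- k = 3: 3 × 0.354/46 = 2.3 to 3 × 0.500/46 = 3.3 percentage points.

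These differences apply to pattern 1 only.

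**The case against.** The strongest reply is that the conflicting case is rare and the stakes are low.

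- **Rarity.** Response is derived from target, non-target and new-lesion data, and Section 7.1.3 says a missing component leaves it underived. Without a baseline there is also no reference sum. Under the exponential assumption, the chance of an event by Day 57 is 1 − 2^(−1.87/4) = 28% to 1 − 2^(−1.87/6) = 19%. If PD is unrelated to missing baseline data, k = 1 to 3 would imply about 1/0.28 = 4 to 3/0.19 = 16 of 46 subjects without baseline data, and nothing in the SAP suggests that. This stands: the figures above are illustrations, and zero is a realistic value. It does not remove the contradiction, because row 4 itself presupposes that PD can be seen in such a subject.
- **Priority of the table.** Section 3.4.2.4 points to the table for the censoring guidance. That gives it some weight, but it is not a precedence clause. Nor does row 1's deferral to rules below it rescue the paragraph: if the paragraph overrode row 1, row 4's condition on PD would do nothing.
- **Stakes.** PFS is secondary and descriptive. The primary endpoint is ORR. The interim rules use the response-evaluable population, which requires a baseline assessment (Table 3.2-1, Section 4). This stands.

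A reader might also infer more than the SAP supports:
- That the rules disagree for all subjects without baseline data. Patterns 4 and 5 agree.
- That they certainly conflict in both directions. The early-death mismatch exists only under reading A, and the paragraph's own death exception for both groups favors reading B.
- That the paragraph always gives the better PFS. Under reading A it counts deaths that the table censors.
- That duration of response is affected. Subjects with missing baseline lesion data are non-evaluable for best overall response (Section 3.4.2.1), so they cannot be the confirmed responders to whom Section 3.4.2.3 limits that endpoint.

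**Conclusion.** The contradiction is real but narrow. It is certain for one pattern: no baseline assessment, PD at the first post-baseline assessment, and no death before the second. The table makes this an event at about 1.9 months if PD falls on Day 57. The paragraph censors it at 0.03 months and so departs from the SAP's own PFS definition. For early death without PD, the row is ambiguous rather than demonstrably in conflict.

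The effect on the PFS estimates is limited to the few subjects, possibly none, without baseline data. Each affected subject would move 6-month PFS by about 1 percentage point in an arm of 46 under the assumed medians of 4 to 6 months. The correction is worth making because the plan contains two incompatible instructions, one of which drops a documented progression.

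**What to change.** State one rule in both the table row and the paragraph. Censor at first dose if either:
- baseline lesion data are missing, AND there is no PD at the first post-baseline assessment, AND there is no death before the second scheduled assessment; or
- there is no post-dose assessment, AND there is no death before the second scheduled assessment.

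Otherwise PD or death counts on its own date, subject to the other censoring rows of Table 3.4.2-1. In practice this adds the death condition to the first limb of row 4, which removes the ambiguity, and the PD condition to the paragraph. It also settles pattern 6, where the PD date applies. Use one term for missing baseline data in both places, and say whether partly missing lesion data are included.

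This rule still censors at first dose a no-baseline subject whose PD first appears at the second or a later assessment, as both texts do now. It reconciles the texts and does not otherwise change the censoring policy.

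The cost is about two sentences of SAP wording. The downside is that PFS may look slightly less favorable than under the paragraph as written.

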### **7.1.3 Visit Disease Response per RECIST1.1**

Investigator visit disease response will be programmatically derived on the data collection instrument using RECIST 1.1 criteria based upon target lesion response, non-target lesion response, and new lesion data. Missing values in any of target lesion response, non-target lesion response, and new lesion data will result in the disease response not being derived.

Possible values include:

- CR – Complete Response

- PR – Partial Response
- SD – Stable Disease
- PD – Progressive Disease
- NE – Non-evaluable

Target Lesion Response	Non-Target Lesion Response	New Lesion	Derived RECIST Disease Response
CR	CR or NA	No	CR
CR	Non-CR/Non-PD or NE	No (or NE)	PR
PR	CR or Non-CR/Non-PD or NE or NA	No (or NE)	PR
SD	CR or Non-CR/Non-PD or NE or NA	No (or NE)	SD
PD	Any	Any	PD
Any	PD	Any	PD
Any	Any	Yes	PD
NE	CR or Non-CR/Non-PD or NE or NA	No	NE
NA	CR	No	CR
NA	Non-CR/Non-PD	No	SD (Non-CR/Non-PD) a
NA	NE or NA	No (or NE)	NE
NA	CR or Non-CR/Non-PD	NE	SD (Non-CR/Non-PD) a

a Per RECIST 1.1, “SD (Non-CR/Non-PD)” is preferred over “SD” for non-target disease since SD is increasingly used as endpoint for assessment of efficacy in some trials so to assign this category when no lesions can be measured is not advised.

If a subject has a missing tumor measurement at some assessment(s) for 1 or more target lesions and criteria for PD are not otherwise met, an overall response of NE will be assigned for the assessment(s).

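### The SAP's definition of an adequate assessment rejects visits that Appendix 7.1.3 scores as PR or SD, and the PFS and DOR censoring texts differ, so an ongoing responder can be censored before the response began

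*SAP*

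**What the plan says.** For subjects without an event, the SAP gives these censoring rules.

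- **PFS, text of Section 3.4.2.4:** patients alive without progression "will be censored at the time of the latest date of assessment from their last evaluable RECIST 1.1 assessment".
- **PFS, Table 3.4.2-1:** the date is "Date of last adequate progression-free disease assessment".
- **PFS, closing paragraph of Section 3.4.2.4:** subjects without progression or death "will be censored for PFS at the date of their last adequate disease assessment". Adequate means measurements for all target lesions recorded at "baseline and a non-NE non-target lesion response". A parenthesis then explains this, in garbled wording, as the last assessment that is neither missing nor non-evaluable.
- **DOR, Section 3.4.2.3, first rule:** "DoR will be censored at the last tumor assessment date", with no condition on the quality of the assessment.
- **DOR, Section 3.4.2.3, second rule:** "The date of PD/death or censoring is the same as defined for PFS".

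The visit response comes from the table in Appendix 7.1.3. In the rows for target PR and target SD, the permitted non-target responses are "CR or Non-CR/Non-PD or NE or NA", and the visit is scored PR or SD respectively. Target CR with non-target NE is scored PR.

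**The concern.** A visit with target PR and non-target NE has a visit response of PR. It can start a response, or confirm one under Section 3.4.2.1, and so counts towards ORR. The same visit fails the literal definition of adequate and cannot serve as a censoring date. DOR starts at the first documentation of a response that is later confirmed, and one of its two censoring rules takes the PFS date. Nothing in the SAP stops that date from falling before the start date.

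At stake are the follow-up credited to some censored subjects in PFS and DOR, and whether every DOR value is valid. A negative duration has no meaning in a Kaplan-Meier analysis, so the programmer would have to settle it by a decision that the plan does not contain. In an open-label trial with investigator-assessed response, that decision is better fixed beforehand.

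**Working it through.** There is no figure in the SAP to reproduce. The check applies the SAP's own formulas to visit patterns.

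**Inputs**
- DOR in months = (censoring date - first response date + 1) / (365.25/12), from Section 3.4.2.3. The divisor is 30.4375.
- PFS in months = (censoring date - first dose date + 1) / 30.4375, from Section 3.4.2.4. With first dose on Day 1, the numerator is the study day of censoring.
- The first post-dose assessment is on Day 57 ± 3, and confirmation is at least 4 weeks after first response (Section 3.4.2.1).
- Two assessments span 16 weeks (notes to Table 3.4.2-1), which is 8 weeks each. Constant spacing, hence Days 57, 113, 169 and 225, is an assumption.
- An unmeasured target lesion makes the target response NE unless PD is already met (Appendix 7.1.1). Every visit with target CR, PR or SD therefore has all target lesions measured, and only the non-target condition can reject it.

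**Example 1.** SD on Day 57 with non-targets evaluated; PR with non-target NE on Days 113 and 169; alive without PD at cutoff. The response is confirmed and starts on Day 113.

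| Censoring rule | Day | DOR | PFS |
|---|---|---|---|
| Last adequate, literal | 57 | 57 - 113 + 1 = -55 days (-1.81 months) | 57/30.4375 = 1.87 months |
| Last evaluable | 169 | 169 - 113 + 1 = +57 days (+1.87 months) | 169/30.4375 = 5.55 months |
| Last tumor assessment (DOR only) | 169 | +57 days (+1.87 months) | not a PFS rule |

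The two PFS dates differ by 169 - 57 = 112 days.

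**Example 2.** As Example 1, with a further visit on Day 225 whose overall response is NE. The rules now give three dates for DOR:
- last tumor assessment, Day 225: 225 - 113 + 1 = 113 days, +3.71 months;
- last evaluable, Day 169: +1.87 months;
- last adequate, Day 57: -1.81 months.

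**How general is this?** All non-PD combinations of target response (CR, PR, SD, NE) and non-target response (CR, Non-CR/Non-PD, NE) over four visits were listed, with no new lesion. Where no visit was adequate, the censoring date was set to Day 1 (an assumption). Of 14,256 patterns with a confirmed response, DOR is zero or negative in none under last tumor assessment, none under last evaluable, and 688 under last adequate. In all 688, every visit from response onset onward fails the adequate test. All three dates differ in 864 patterns. These counts show what is possible. They are not frequencies.

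**The case against.** The SAP supplies some of the ordering. Section 3.4.2.4 refers the reader to the table for the censoring date. Section 3.4.2.3 ties DOR to PFS. Section 3.4.3 says that the censoring guidance applies uniformly to all RECIST-based efficacy analyses. The parenthesis after the adequate definition suggests that adequate was meant as evaluable, and on that reading the negative DOR disappears. Appendix 7.1.5, which dates an SD assessment for censoring purposes, also points to the visit response as the basis. These are fair indications of intent. They do not settle the text, because the parenthesis contradicts the definition that it explains and the two DOR sentences still differ.

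A reader might infer that every rejected visit costs 8 weeks of follow-up. That is not so. Censoring is at the last adequate assessment, so a rejected visit followed by an adequate one costs nothing, and only a run of rejected visits lasting to cutoff loses time. Subjects with no non-target lesions at baseline have NA, not NE, and are untouched. Where only some non-target lesions are unevaluable and none shows unequivocal progression, Appendix 7.1.2 still allows Non-CR/Non-PD.

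Finally, requiring evaluable non-target disease before crediting progression-free time is a defensible conservative choice. That stands as a reason for a sensitivity analysis. It does not justify counting a visit as a response while refusing it for the duration of that response.

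**Conclusion.** The point holds as an inconsistency to be corrected before the analysis. The literal definition of adequate and its gloss select different visits, PFS has two censoring terms, and DOR has two censoring rules. Following the table and the literal definition can produce an impossible DOR (-55 days in the example, against +57) and PFS censored 112 days early.

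A negative DOR needs four things together: a confirmed responder without PD or death at cutoff; every visit from onset onward failing the adequate test; the definition preferred to its gloss; and the PFS-linked DOR sentence applied. One adequate visit at or after onset removes the negative value, although DOR can still be shortened. The case is probably uncommon, and the SAP gives no rate of non-target NE from which to estimate it.

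It would be tempting to conclude that the differing texts will give different median PFS or DOR. The SAP does not support that: the medians may or may not change, and no effect on them is shown. PFS and DOR are secondary endpoints summarized by Kaplan-Meier. The primary ORR and the response-based interim analyses in Section 4 do not use these dates.

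**What to change.** Use one censoring date for PFS and DOR in subjects without an event: the last assessment whose derived visit response in Appendix 7.1.3 is CR, PR, SD or SD (Non-CR/Non-PD).

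- Replace the adequate definition in the closing paragraph of Section 3.4.2.4 with this rule, and remove the parenthesis.
- Use the same term in the opening text of Section 3.4.2.4 and in Table 3.4.2-1.
- In Section 3.4.2.3, delete the rule based on the last tumor assessment and keep the link to PFS.

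Under this rule Example 1 gives DOR of +1.87 months, and no pattern in the listing gives a zero or negative value.

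The cost is SAP wording and one derivation flag, with no new data. There is a small downside: some visits with non-target or new-lesion status NE are credited as progression-free, as they already are for response. A sensitivity analysis with the stricter definition, and with DOR censored no earlier than response onset, can show how much this matters.
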